7.3 Legal Risks – There are no legal risks associated with this protocol

7.4 Economic Risks – There are no economic risks associated with this protocol. Any costs that are not part of the patient's standard of care for brachytherapy and standard follow-up will be paid for by research funds.

7.5 Privacy/Confidentiality Risks – All research personnel involved in this trial will comply with HIPAA regulations. Because the data that is collected will contain personally identifiable information the following measures will be taken to minimize the risk of breaching patient confidentiality:

- Patients' clinical data (hard and soft copies) will be stored in locked confidential files in the Radiation oncology protocol office at Johns Hopkins east Baltimore campus, and on encrypted, restricted-access servers within the Radiation Oncology domain.
- Only the study personnel, the Johns Hopkins Clinical Research Office, the Office of Human Research Protection (OHRP), the Johns Hopkins Institutional Review Board, and other regulatory agencies will have access to the study files. The secured Clinical data includes: case report forms, source documentation, signed consent forms, and any material containing patient identifying information.
- This data will be securely stored in the Radiation Oncology protocol office at Johns Hopkins as long as required by governmental regulations.
- All of the agencies noted above who have access to study documents and patient identifier codes are to keep the identity of all subjects on this trial confidential. No information by which patients can be identified will be published.

7.6 Benefits – There is no expectation that patients will benefit from their participation in this study. There is the potential benefit that through participation subjects in the Flutamide arm will receive treatment that is more effective against their prostate cancer.

7.7 Payments and Compensation – Patients will not be paid or compensated for their participation in this trial.

8.0 Reporting of Serious or Unexpected Adverse Events

This is a research trial that is studying the feasibility and practicability of a new treatment planning system for patients who undergo brachytherapy. There are no expected adverse events associated with this trial. However, the research team will be conducting post-follow-ups on all patients enrolled onto this trial as outlined in section 4.7 and will report any adverse events that are either unexpected or are serious.

"CTCAE term (AE description) and grade: The descriptions and grading scales found in the revised NCI Common Terminology Criteria for Adverse Events (CTCAE) version 4.0 will be utilized for all AE reporting. All appropriate treatment areas should have access to a copy of the CTCAE version 4.0."

8.1 The following guidelines will be followed for reporting serious or unexpected adverse events:

a). All **fatal** events, both **anticipated and unanticipated**, must be reported to the JHM IRB within three (3) working days after the PI learns of the event, whether or not the PI believes the event to be related to the study. All other events, which are both **serious** and **unanticipated**, must be reported to the JHMI IRB within three (3) working days after the PI learns of the event. Events which are **serious** but **anticipated**, should be reported as part of the continuing review application. If any of these Serious Adverse Events requires a change to the protocol or consent form, the PI must make those changes promptly and submit the revised documents to the JHM IRB.

b) **Important** Adverse Events that are **unanticipated** must be reported to the JHM IRB within (10) ten working days. If the Important Adverse Event requires changes to the protocol or consent form, the PI must make those changes promptly and submit the revised documents to the JHM IRB.

C) All other **unanticipated** Adverse Events or changes to the protocol and consent form must be reported to the JHM IRB as follows:

1. If the event affects the risk/benefit ratio for study subjects, the reporting requirement is *promptly*.
2. If the event does not affect the risk/benefit ratio for study subjects, the reporting requirement is *at least annually* through the continuing review application.

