4.0 Protocol Design

This will be a prospective, single-center, two-phase study to assess the efficacy of single pulsed-dose Flutamide in creating DSBs in prostate cancer within patients receiving central androgen suppression and brachytherapy. The initial phase is a 6-patient single-arm run-in phase to test feasibility and rule out futility of the intervention. All patients within the run-in phase will receive 250mg Flutamide prior to brachytherapy and prostatic biopsy. Biostatistician will be consulted upon completion of run-in phase. If futility is ruled out (>1 patients with DSBs on biopsy), then accrual will continue in the randomized, double-blind phase. Subjects will be randomized in a 2:1 ratio (12:6 patients), for total of 18 patients randomized receiving Flutamide and 6 patients receiving placebo. Thus, total evaluable patients including both phases (non-randomized/run-in plus randomized) will be 24 patients, with 30 enrolled to ensure minimum of 24 evaluable.

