7.0 Risks/Benefits Assessment

Patients enrolled onto this trial would undergo brachytherapy under anesthesia whether or not they participate in this trial. Therefore, the risks that are associated with the brachytherapy are not risks associated with the research. Similarly, we will only enroll patients who are undergoing androgen suppression as standard of care based on disease characteristics. Furthermore, patients would undergo the standard pre-treatment and post-treatment assessments/studies that are outlined in section 4.7 whether or not they participate in this trial.

Transperineal biopsy under anesthesia – Patient will undergo partial-gland transperineal biopsies as a result of enrollment on this trial. The risks of these biopsies is similar to that of standard prostate biopsies but with less chance of infection or sepsis due to not accessing through the rectum, as well as only targeting regions of known involvement. For comparative purposes, patients who undergo active surveillance have yearly biopsies performed for up to several years in succession until progression, therefore 1 partial-gland biopsy associated with this protocol is relatively modest.

Risk of Flutamide – Flutamide is an FDA approved drug with indication for use in patients with prostate cancer. Since we are only giving a single 250mg dose of Flutamide (compared to standard daily 250mg TID dosing for 4 months or more), it is a very low likelihood that patients will experience any long-lasting toxicity. It is theoretically possible that patients could have an acute adverse reaction, although this is expected to be rare.

Risk of blood draw

Patients will undergo blood sampling prior to the biopsy for pharmacokinetic analysis; patients who opt to participate in the exploratory endpoints will have additional blood draws. There could be pain or unexpected excessive bleeding and/or swelling related to the blood draw(s).

7.1 Psychological Risks - There are no foreseeable psychological risks associated with this protocol.

7.2 Social Risks – There are no foreseeable social risks associated with this protocol

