8.2 Definitions

Serious Adverse Event: means an event that is

- fatal
- life-threatening
- persistent or significantly disabling or incapacitating
- inpatient hospitalization or prolongation of hospitalization
- congenital anomaly or defect and/or
- a significant medical incident (considered to be a serious study related event because, based upon appropriate medical judgment, it may jeopardize the subject and may require medical or surgical intervention to prevent one of the outcomes listed in this definition.)

Important Adverse Event: means an event, although not a Serious Adverse Event, which still presents an undesirable occurrence that interferes with the subject's usual activities and may be persistent or require treatment. (For example, serious rash, cough, or fever.)

Unanticipated Adverse Event: means an event that results from a study intervention and was not expected or anticipated from prior experience. This includes expected events that occur with greater frequency or severity than predicted from prior experience.

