Race There are no known alterations in Flutamide absorption, distribution, metabolism, or excretion due to race.

Renal Impairment Following a single 250 mg dose of Flutamide administered to subjects with chronic renal insufficiency, there appeared to be no correlation between creatinine clearance and either Cmax or AUC of Flutamide. Renal impairment did not have an effect on the Cmax or AUC of the biologically active alpha-hydroxylated metabolite of Flutamide. In subjects with creatinine clearance of < 29 mL/min, the half-life of the active metabolite was slightly prolonged. Flutamide and its active metabolite were not well dialyzed. Dose adjustment in patients with chronic renal insufficiency is not warranted.

Hepatic Impairment No information on the pharmacokinetics of Flutamide in hepatic impairment is available (see **BOXED WARNING, Hepatic Injury**).

Women, Pediatrics Flutamide has not been studied in women or pediatric subjects. **Drug-Drug Interactions**

Interactions between Flutamide capsules and LHRH-agonists have not occurred. Increases in prothrombin time have been noted in patients receiving warfarin therapy (see **PRECAUTIONS**).

Clinical Studies

Flutamide has been demonstrated to interfere with testosterone at the cellular level. This can complement medical castration achieved with LHRH-agonists which suppresses testicular androgen production by inhibiting luteinizing hormone secretion.

The effects of combination therapy have been evaluated in two studies. One study evaluated the effects of Flutamide and an LHRH-agonist as neoadjuvant therapy to radiation in stage B2-C prostatic carcinoma and the other study evaluated Flutamide and an LHRH-agonist as the sole therapy in stage D2 prostatic carcinoma.

Stage B2-C Prostatic Carcinoma

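### Section 8.0 describes a different study, conflicts with Section 7.0 on expected adverse events and cites a missing Section 4.7, and no scheduled contact carries an adverse event assessment

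*Combined protocol and SAP*

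**What the plan says.** Section 8.0 opens by stating that the trial is "studying the feasibility and practicability of a new treatment planning system" for brachytherapy patients. It continues: "There are no expected adverse events associated with this trial". It then promises follow-up of every enrolled patient "as outlined in section 4.7", with unexpected or serious events to be reported.

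Section 4.0 describes something else: a study "to assess the efficacy of single pulsed-dose Flutamide in creating DSBs in prostate cancer". Sections 5.1 and 5.3 set out a single oral dose of flutamide or placebo 6 to 12 hours before brachytherapy, and a transperineal research biopsy of at most 12 cores. Section 5.2.1 adds blood sampling for the drug metabolite.

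Section 7.0 attaches risks to each of these. For flutamide: "It is theoretically possible that patients could have an acute adverse reaction", though this is thought to be rare. For the biopsy: "The risks of these biopsies is similar to that of standard prostate biopsies", with a lower chance of infection. For blood draws it names pain, bleeding and swelling.

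**The concern.** Section 8.0 is the text that staff follow when an event occurs. It misdescribes what is being studied and denies that any event is expected, while the preceding section describes several. The reporting rules that follow depend on exactly that distinction. The section also points to a missing place for the follow-up that would bring events to light.

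Two things are at stake. The first is whether similar events in different patients are reported to the IRB by the same route. The second is whether events after the dose and biopsy are sought at defined times and in the same way in both randomized arms, or recorded only when someone happens to mention them.

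**Working it through.** No arithmetic applies. The check sets the sections side by side.

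**1. Which study is described.** The goal (end of Section 1.0), objectives (2.0), design (4.0) and statistical section (6.1) all concern DNA double strand breaks after pulse-dose flutamide. None mentions a treatment planning system. The opening sentence of 8.0 therefore belongs to another protocol.

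**2. What is expected.** Section 8.0 expects nothing; Section 7.0 describes risks of three research procedures. Section 7.0 is narrative, however. It gives no event terms for flutamide, and it mentions infection and sepsis after biopsy only by comparison with the transrectal route. Section 9.0 covers pharmacology, indications and contraindications. It refers the reader to "BOXED WARNING, Hepatic Injury", but neither that text nor a list of adverse reactions appears in the protocol body.

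**3. What follows for reporting.** Section 8.2 says an unanticipated event "means an event that results from a study intervention and was not expected or anticipated from prior experience". It adds expected events that prove more frequent or more severe than predicted, which presupposes a statement of what was predicted. Applying 8.1 to a known type of biopsy or drug event under the two readings:

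| Event | Reading 8.0 (nothing anticipated) | Reading 7.0 with 8.2 (anticipated) |
|---|---|---|
| Fatal | 3 working days | 3 working days |
| Serious, non-fatal | 3 working days | continuing review |
| Important, not serious | 10 working days | no route stated in 8.1 |

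The fatal route is the same either way. The other two depend on which section the reader believes.

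**4. The follow-up reference.** Section 4 runs from 4.1 to 4.6, and 5.0 comes next. Section 4.7 is cited twice, in 7.0 and in 8.0. Section 4.6 also cites itself as a place where procedures are outlined, so renumbering is the likely cause. The intended targets are probably the calendar in 4.5 and the follow-up in 5.4.

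**5. Whether those targets would serve.** The scheduled contacts from dosing onward are:

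- Implant day, 6 to 12 hours after the dose: biopsy, implant and a plasma hydroxyflutamide sample.
- 4 weeks (±7 days): PSA and testosterone, with optional plasma and urine.
- 6 months (±45 days): the same as at 4 weeks.

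The calendar has no adverse event row. Section 5.4 adds only assessment under routine practice and specimen collection. Section 4.6 defines the trial data as the results of procedures in 4.5 and 4.6, which again do not include adverse events. Section 8.3 starts once an event is already known. Correcting the number 4.7 would therefore lead the reader to sections that schedule no adverse event assessment.

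**The case against.** The best defence is that these are template leftovers and that the working parts of the safety plan do not rely on them. Much of this stands. CTCAE version 4.0 grading, definitions of serious and important events, IRB timelines, follow-up to resolution (8.3) and DSMB toxicity review at least annually (16.0) are all present. Safety is not a stated objective, and neither the gammaH2AX endpoint nor the stopping rule in 6.3 is touched.

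Several stronger conclusions are tempting, but the documents do not support them:

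- **That every serious known event would be treated as unanticipated.** Section 8.2 ties expectedness to prior experience, not to the sentence in 8.0. The classification is ambiguous rather than fixed. If 8.0 did govern, the effect would be faster reporting.
- **That patients are not seen until 4 weeks after the dose.** Implant day is a scheduled contact 6 to 12 hours after dosing. What is missing is an adverse event assessment marked at it.
- **That relatedness would be judged against the wrong intervention.** Sections 8.2 and 8.3 refer to the study intervention and to study participation, and these are set out in 4.0, 5.1 and 5.3. The stray sentence defines nothing.
- **That the DSMB review is unreliable.** Nothing in Section 16.0 makes it depend on the opening of 8.0.
- **That the trial has no list of expected events anywhere.** Section 4.1 says the consent form will describe potential risks, and that form was not available here. The statement holds for the protocol body only.

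The objection does not remove the conflict between 7.0 and 8.0 on a term that decides the reporting route, or the absence of any scheduled assessment.

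**Conclusion.** The point holds as a defect in safety reporting and in the collection of adverse events. Section 8.0 carries another study's description. Its statement that nothing is expected contradicts 7.0, and the same serious, non-fatal event can take a 3-working-day route or wait for continuing review. The follow-up reference is dead in both places where it is used. None of the three existing contacts from dosing onward carries an adverse event assessment, so collection rests on routine practice and on events that come to notice by themselves. This applies to all 30 planned enrolments, including the 24 needed as evaluable.

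The size should not be inflated: general safety handling is in place, and no efficacy or feasibility conclusion changes. The point should be corrected, but it does not threaten the trial's primary result. The conclusion assumes that the protocol body is what staff follow and that no separate safety manual or case report form instruction supplies the missing schedule. The documents mention none.

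**What to change.** Four text changes are needed:

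1. Replace the first two sentences of 8.0 with the actual research interventions: a single study-drug dose, research transperineal biopsy and blood draws.
2. Reconcile the expectedness statement with 7.0 by stating the anticipated events, with the investigators supplying the specific flutamide and biopsy terms. Pointing to 7.0 alone is not enough, because it names no flutamide events.
3. Correct both references to 4.7, in 7.0 and 8.0, to the sections that exist (4.5 and 5.4).
4. Add one adverse event assessment row to the 4.5 calendar at the existing implant-day, 4-week and 6-month contacts, completed in the same way in both randomized arms.

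The cost is a protocol amendment and one more data item at visits already scheduled. No visit is added, and the sample size and stopping rule stay as they are. Whether any further clinical or laboratory monitoring is needed is for the investigators to decide.

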8.2 Definitions

Serious Adverse Event: means an event that is

- fatal
- life-threatening
- persistent or significantly disabling or incapacitating
- inpatient hospitalization or prolongation of hospitalization
- congenital anomaly or defect and/or
- a significant medical incident (considered to be a serious study related event because, based upon appropriate medical judgment, it may jeopardize the subject and may require medical or surgical intervention to prevent one of the outcomes listed in this definition.)

Important Adverse Event: means an event, although not a Serious Adverse Event, which still presents an undesirable occurrence that interferes with the subject's usual activities and may be persistent or require treatment. (For example, serious rash, cough, or fever.)

Unanticipated Adverse Event: means an event that results from a study intervention and was not expected or anticipated from prior experience. This includes expected events that occur with greater frequency or severity than predicted from prior experience.

8.3 Following a Study Related Adverse Event

If a patient experiences an adverse event while on study, the following steps will be taken:

- 1) Establish the cause and severity of the adverse event and determine if said event is related to study participation.
- 2) Principal Investigator will decide what treatment(s), if any, is/are required.
- 3) Depending on the type and severity of adverse event, an appropriate follow-up schedule will be constructed which will allow for determination of event outcome.
- 4) Patient will be followed by principal investigator until the adverse event has resolved.

[figure not shown]
9.0 Description of the Drug

Flutamide is approved by the US Food and Drug Administration for use in patients with (Jewett) stage B2-C prostate cancer (i.e. AJCC stage T1c – T3b), in conjunction with androgen deprivation and radiation therapy.

Flutamide Description

Flutamide capsules contain Flutamide, an acetanilid, nonsteroidal, orally active antiandrogen having the chemical name, α,α,α -trifluoro-2-methyl-4'-nitrom-propionotoluidide.

Each capsule contains 125 mg Flutamide. The compound is a buff to yellow powder with a molecular weight of 276.22 and the following structural formula:

C11H11F3N2O3

In addition, each capsule contains the following inactive ingredients: corn starch, lactose monohydrate, magnesium stearate, povidone, and sodium lauryl sulfate. Gelatin capsule shells may contain gelatin, silicon dioxide, sodium lauryl sulfate, titanium dioxide, FDA/E172 Red Iron Oxide, FDA/E172 Yellow Iron Oxide, and black ink containing pharmaceutical glaze (modified) in SD-45, synthetic black iron oxide, Nbutyl alcohol, SDA-3A alcohol, FD&C Blue No.2 Aluminum Lake, FD&C Red No.40 Aluminum Lake, FD&C Blue No.1 Aluminum Lake, and D&C Yellow No.10 Aluminum Lake.

Clinical Pharmacology General

In animal studies, Flutamide demonstrates potent antiandrogenic effects. It exerts its antiandrogenic action by inhibiting androgen uptake and/or by inhibiting nuclear binding of androgen in target tissues or both.

Prostatic carcinoma is known to be androgen-sensitive and responds to treatment that counteracts the effect of androgen and/or removes the source of androgen, e.g., castration. Elevations of plasma testosterone and estradiol levels have been noted following Flutamide administration. **Pharmacokinetics**

Absorption

Analysis of plasma, urine, and feces following a single oral 200 mg dose of tritium-labeled Flutamide to human volunteers showed that the drug is rapidly and completely absorbed. Following a single 250 mg oral dose to normal adult volunteers, the biologically active alpha-hydroxylated metabolite reaches maximum plasma concentrations in about 2 hours, indicating that it is rapidly formed from Flutamide. Food has no effect on the bioavailability of Flutamide.

Distribution

In male rats administered an oral 5 mg/kg dose of ¹⁴C-Flutamide neither Flutamide nor any of its metabolites is preferentially accumulated in any tissue except the prostate. Total drug levels were highest 6 hours after drug administration in all tissues. Levels declined at roughly similar rates to low levels at 18 hours. The major metabolite was present at higher concentrations than Flutamide in all tissues studied. Following a single 250 mg oral dose to normal adult volunteers, low plasma concentrations of Flutamide were detected. The plasma half-life for the alpha-hydroxylated metabolite of Flutamide is approximately 6 hours. Flutamide, *in vivo*, at steady-state plasma concentrations of 24 to 78 ng/mL, is 94% to 96% bound to plasma proteins. The active metabolite of Flutamide, *in vivo*, at steady-state plasma concentrations of 1556 to 2284 ng/mL, is 92% to 94% bound to plasma proteins. **Metabolism**

The composition of plasma radioactivity, following a single 200 mg oral dose of tritium-labeled Flutamide to normal adult volunteers, showed that Flutamide is rapidly and extensively metabolized, with Flutamide comprising only 2.5% of plasma radioactivity 1 hour after administration. At least six metabolites have been identified in plasma. The major plasma metabolite is a biologically active alphahydroxylated derivative which accounts for 23% of the plasma tritium 1 hour after drug administration.

The major urinary metabolite is 2-amino-5nitro-4-(trifluoromethyl)phenol.

Excretion

Flutamide and its metabolites are excreted mainly in the urine with only 4.2% of a single dose excreted in the feces over 72 hours.

Plasma Pharmacokinetics of Flutamide and HydroxyFlutamide in Geriatric Volunteers (mean \pm SD)

	Single Dose Flutamide	HydroxyFlutamide	Steady- State Flutamide	HydroxyFlutamide
Cmax (ng/mL)	25.2 \pm 34.2	894 \pm 406	113 \pm 213	1629 \pm 586
Elimination half-life (hr)	---	8.1 \pm 1.3	7.8	9.6 \pm 2.5
Tmax (hr)	1.9 \pm 0.7	2.7 \pm 1.0	1.3 \pm 0.7	1.9 \pm 0.6
Cmin (ng/mL)	---	---	---	673 \pm 316

Special Populations

Geriatric Following multiple oral dosing of 250 mg t.i.d. in normal geriatric volunteers, Flutamide and its active metabolite approached steady-state plasma levels (based on pharmacokinetic simulations) after the fourth Flutamide dose. The half-life of the active metabolite in geriatric volunteers after a single Flutamide dose is about 8 hours and at steady-state in 9.6 hours.

Race There are no known alterations in Flutamide absorption, distribution, metabolism, or excretion due to race.

Renal Impairment Following a single 250 mg dose of Flutamide administered to subjects with chronic renal insufficiency, there appeared to be no correlation between creatinine clearance and either Cmax or AUC of Flutamide. Renal impairment did not have an effect on the Cmax or AUC of the biologically active alpha-hydroxylated metabolite of Flutamide. In subjects with creatinine clearance of < 29 mL/min, the half-life of the active metabolite was slightly prolonged. Flutamide and its active metabolite were not well dialyzed. Dose adjustment in patients with chronic renal insufficiency is not warranted.

Hepatic Impairment No information on the pharmacokinetics of Flutamide in hepatic impairment is available (see **BOXED WARNING, Hepatic Injury**).

Women, Pediatrics Flutamide has not been studied in women or pediatric subjects. **Drug-Drug Interactions**

Interactions between Flutamide capsules and LHRH-agonists have not occurred. Increases in prothrombin time have been noted in patients receiving warfarin therapy (see **PRECAUTIONS**).

Clinical Studies

Flutamide has been demonstrated to interfere with testosterone at the cellular level. This can complement medical castration achieved with LHRH-agonists which suppresses testicular androgen production by inhibiting luteinizing hormone secretion.

The effects of combination therapy have been evaluated in two studies. One study evaluated the effects of Flutamide and an LHRH-agonist as neoadjuvant therapy to radiation in stage B2-C prostatic carcinoma and the other study evaluated Flutamide and an LHRH-agonist as the sole therapy in stage D2 prostatic carcinoma.

Stage B2-C Prostatic Carcinoma

The effects of hormonal treatment combined with radiation was studied in 466 patients (231 Flutamide capsules + goserelin acetate implant + radiation, 235 radiation alone) with bulky primary tumors confined to the prostate (stage B2) or extending beyond the capsule (stage C), with or without pelvic node involvement. In this multicentered, controlled trial, administration of Flutamide capsules (250 mg t.i.d.) and goserelin acetate (3.6 mg depot) prior to and during radiation was associated with a significantly lower rate of local failure compared to radiation alone (16% vs. 33% at 4 years, $P < 0.001$). The combination therapy also resulted in a trend toward reduction in the incidence of distant metastases (27% vs. 36% at 4 years, $P = 0.058$). Median disease-free survival was significantly increased in patients who received complete hormonal therapy combined with radiation as compared to those patients who received radiation alone (4.4 vs 2.6 years, $P < 0.001$). Inclusion of normal PSA level as a criterion for disease-free survival also resulted in significantly increased median disease-free survival in patients receiving the combination therapy (2.7 vs. 1.5 years, $P < 0.001$).

Stage D2 Prostatic Carcinoma

To study the effects of combination therapy in metastatic disease, 617 patients (311 leuprolide + Flutamide, 306 leuprolide + placebo) with previously untreated advanced prostatic carcinoma were enrolled in a large multicentered, controlled clinical trial.

Three and one-half years after the study was initiated, median survival had been reached. The median actuarial survival time was 34.9 months for patients treated with leuprolide and Flutamide versus 27.9 months for patients treated with leuprolide alone. This 7 month increment represents a 25% improvement in overall survival time with the Flutamide therapy. Analysis of progression-free survival showed a 2.6 month improvement in patients who received leuprolide plus Flutamide, a 19% increment over leuprolide and placebo.

Indications and Usage for Flutamide

Flutamide capsules are indicated for use in combination with LHRH-agonists for the management of locally confined Stage B2-C, and Stage D2 metastatic carcinoma of the prostate. **Contraindications**

Flutamide capsules are contraindicated in patients who are hypersensitive to Flutamide or any component of this preparation.

Flutamide capsules are contraindicated in patients with severe hepatic impairment (baseline hepatic enzymes should be evaluated prior to treatment).

